## 1.0 OBJECTIVES

The purpose of this protocol is to test the effect of statin therapy, as compared to placebo, on the cardiac dysfunction after administration of anthracyclines among patients with lymphoma.

Anthracyclines are a mainstay of cancer treatment with more than 100,000 patients treated per year with anthracyclines in the United States; however, their use is associated with increased rates of heart failure and left ventricular (LV) dysfunction. Once anthracycline-induced cardiotoxicity (AIC) is symptomatic, survival is dramatically decreased. There is significant scientific plausibility and supportive observational data that statins may protect the heart during the administration of anthracyclines. STOP-CA (Statins TO Prevent the Cardiotoxicity from Anthracyclines) is a multi-center randomized double-blind placebo controlled trial, in 270 statin-naive patients who will be randomized 1:1 to atorvastatin 40mg/daily or placebo to determine whether atorvastatin started prior to anthracyclines reduces anthracycline-induced cardiotoxicity (AIC) among patients with newly diagnosed lymphoma. The endpoint AIC is defined based on expert consensus as a  $\geq 10\%$  reduction in LVEF to  $< 55\%$  within the first 12 months after therapy. LVEF will be measured using the gold-standard, cardiac magnetic resonance (CMR), performed in an established core clinical trials laboratory by expert readers. Participants will be recruited over 3 years from large volume academic oncology networks. Myocardial fibrosis is a key intermediary that occurs prior to the development of LV dysfunction. CMR is the gold-standard imaging technique for fibrosis; therefore, to test whether the sub-acute development of myocardial fibrosis can predict the late occurrence of AIC and whether statins reduce myocardial fibrosis, we also propose measuring the extent of fibrosis at baseline and 6 months. We hypothesize that statins will attenuate myocardial fibrosis and that the extent of early fibrosis will predict the decrease in LVEF at 12 months. Both echocardiography and serum troponin are more widely available than CMR; therefore, in a third aim, we will test whether strain by echocardiography and troponin levels measured early during chemotherapy (after 4 of 8 standard cycles,  $\approx 3$  months), can identify patients at high risk of AIC.

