### 1.3 Secondary Objectives

Number 1: To compare the effect of statins, vs. placebo, on the development of myocardial fibrosis after anthracyclines. In a sub-study of 80 patients from Aim 1 (n=40 in each arm), we will measure myocardial fibrosis by calculation of the myocardial extracellular volume (ECV) using CMR, as previously described, at baseline and 6 months to determine:

- a. Whether statins prevent the anthracycline-induced increase in myocardial fibrosis at 6 months.
- b. Whether a change in fibrosis or LVEF at 6 months predicts the occurrence of AIC at 12 months.

Number 2: We will determine whether an early decrease in myocardial strain or an increase in high-sensitivity troponin *during* anthracyclines (after 4 of 8 standard cycles ( $\approx$  3 months)) can predict subsequent development of AIC at 12 months. We will test:

- a. Whether statins, as compared to placebo, prevent the reduction in strain or the increase in troponin throughout the study period (12 months).
- b. Whether a change in troponin, strain, or both at 3 months predicts AIC at 12 months.
- c. Whether a change in troponin, strain or both at 3 months predicts fibrosis detected by ECV at 6 months.

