#### **Primary End-Point**

**Our primary endpoint will be the proportion of patients in each group that have a decrease of 10% or more in LVEF to <55% from baseline to 12 months after initiation of anthracyclines.**

**Assumptions:** We anticipate that 20% of the patients in the placebo group will reach the primary end-point. This assumption is based on significant prior literature; specifically, Limat *et al.* performed a prospective study where they enrolled patients similar to those proposed in this study (lymphoma receiving anthracycline-based chemotherapy) and performed a baseline measurement of LVEF and a measurement at 1 year. Their primary end-point was a more stringent cut-off than recommended by guidelines or being used in this study, a decrease of >15% in LVEF. They found that 20% of their population had a reduction of >15% in LVEF. Using CMR, two studies have tested the percentage of patients with a significant reduction in LVEF after anthracyclines. In a prospective observational study, Drafts and colleagues found

that 26% of patients decreased their LVEF to <50% and in a prospective randomized study, Bosch and colleagues found that up to 33% of patients decreased their LVEF to <55%. In the single small randomized study which also used 40 mg of atorvastatin with 20 subjects in each arm, there was no decrease in LVEF after anthracyclines among patients on statins. Our base case assumptions are as follows: 20% of the placebo group and 5% of the statin treatment group will meet the primary endpoint and we will be able to enroll 300 patients meeting all inclusion and exclusion criteria. From these, we anticipate a drop-out rate of approximately 10% due to a one year mortality of  $\approx$ 5% and atorvastatin related side-effects in 4% of patients. The remaining 270 patients will provide us with a 98% power to detect a 15% difference in the proportions of those achieving the primary end-point at a one-sided significance level of 0.05. Moreover, we will have a 70% power if the difference in the percentage reaching the primary end-point between groups falls as low as 10%.

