**Specific Aim 2:**

**Determine the effect of statins on myocardial fibrosis.** In a sub-study of 80 patients from Aim 1 (n=40 in each arm), we will measure myocardial fibrosis by calculation of the myocardial extracellular volume (ECV) using CMR, as previously described, at baseline and 6 months to determine:

- c. Whether statins prevent the anthracycline-induced increase in myocardial fibrosis at 6 months as compared to placebo.
- d. Whether a change in fibrosis or LVEF at 6 months predicts the occurrence of AIC at 12 months.

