**Statistical Analysis**

**Aim 2a. Assumptions:** In our retrospective clinical study the ECV in healthy age-matched volunteers was 0.28 and was 0.04 lower than in patients treated previously with anthracyclines (0.32, mean difference and SD:  $0.04 \pm 0.05$ ). Based on these data, with 80 patients (40 from each treatment group) we will have 94% power to detect a treatment difference with a two-sided 0.05 significance level. If the actual difference in the ECV between groups is only 0.03 with a SD of 0.05, then we will still have a 75% power to detect a difference between the groups. We are assuming a 10% drop-out for participants in Aim 1. If we assume the same dropout rate for Aim 2, then our final sample size will be 36 per group. A final sample size of 72 will have a 92% power to detect a treatment difference between the means. **Analysis Plan:** The ECV is a unit-less continuous variable. The change in ECV levels from baseline to 6 months will be compared between the statin- and placebo treated groups using a Student *t* test.

**Aim 2b. Analysis plan:** The predictive value of the change in ECV between 0 and 6 months for the occurrence of the primary end-point of Aim 1 (a reduction in LVEF of  $\geq 10\%$  to less than 55% at 12 months) will be determined using a logistic regression model.

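### Aim 2b tests 6-month ECV change only against binary AIC, on about 9 expected events and without a treatment-arm term; the stated hypothesis about the decrease in LVEF has no planned analysis

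*Protocol*

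**What the plan says.** The fibrosis sub-study takes 80 patients from Aim 1, 40 per arm, with CMR at baseline and 6 months (Protocol 13.1, Specific Aim 2). For attrition it says: "If we assume the same dropout rate for Aim 2, then our final sample size will be 36 per group".

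Objective 1b in Protocol 1.3 is worded as prediction of AIC: "Whether a change in fibrosis or LVEF at 6 months predicts the occurrence of AIC at 12 months". The Aim 2b analysis plan follows it: "The predictive value of the change in ECV between 0 and 6 months for the occurrence of the primary end-point of Aim 1", which is the binary fall in LVEF, "will be determined using a logistic regression model". The plan gives no covariates, event count or power for this analysis.

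Protocol 1.0 states the purpose of the fibrosis measurement as predicting late AIC. It then adds a hypothesis in different terms: "the extent of early fibrosis will predict the decrease in LVEF at 12 months".

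The study calendar (Section 10) schedules MRI at baseline and 12 months for all participants, with an additional 6-month MRI in the sub-study. The SAP stops at Aim 1c and does not cover Aim 2.

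**The concern.** The Section 1.0 hypothesis concerns a quantity, the fall in LVEF. The only planned test of fibrosis as a predictor reduces that quantity to a yes/no threshold that few sub-study patients will cross. The continuous measurement is already collected, by the modality that Section 2.1 A.6 chooses for its low variability.

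The model also has no term for treatment arm. The protocol expects statins to lower both ECV and AIC. Pooling the arms without adjustment therefore lets the treatment effect appear as an association between fibrosis and AIC.

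Two misreadings are at stake. A null result from about 9 events could be taken as evidence that fibrosis does not matter. A positive result could be taken as evidence that fibrosis predicts injury when it partly reflects which drug the patient received.

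**Working it through.** **1. The plan's own figures (Aim 2a).** Power = Φ(Δ / (SD·√(2/n)) − 1.96), with SD 0.05:

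| n per arm | Δ | Normal | t test | Stated |
|---|---|---|---|---|
| 40 | 0.04 | Φ(3.578 − 1.96) = 94.7% | 94.2% | 94% |
| 40 | 0.03 | Φ(2.683 − 1.96) = 76.5% | 75.5% | 75% |
| 36 | 0.04 | Φ(3.394 − 1.96) = 92.4% | 91.7% | 92% |

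All three reproduce. There is no Aim 2b figure to reproduce.

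**2. Expected events in Aim 2b.** The base case in Protocol 13.1 is "20% of the placebo group and 5% of the statin treatment group will meet the primary endpoint". With 36 per arm: 36 × 0.20 + 36 × 0.05 = 7.2 + 1.8 = 9.0 (10.0 if all 40 per arm complete). From the sum of the two binomials, the chance of 6 or fewer events is 18% and of fewer than 10 is 59%. The chance of no event in the statin arm is 0.95^36 = 16%. Other rates with 36 per arm:

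- 20% and 0%: 7.2 events
- 20% and 10%: 10.8
- 33% and 5%: 13.7
- 20% in both arms: 14.4

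**3. What about 9 events can detect.** For one standardised predictor without covariates, 72 patients and an overall event proportion of 9/72 = 0.125, the odds ratio per SD needed for 80% power is exp[(1.96 + 0.842)/√(72 × 0.125 × 0.875)] = exp(2.802/2.806) ≈ 2.7. Power at an odds ratio of 2.0 is Φ(2.806 × 0.693 − 1.96) ≈ 49%. For a continuous outcome, 80% power needs a correlation of tanh(2.802/√69) ≈ 0.33.

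**4. Comparison of models by simulation.** Inputs:

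- 36 patients per arm, with AIC rates set to 20% and 5%.
- ECV change lower by 0.04/0.05 = 0.8 SD in the statin arm, from the Aim 2a assumptions.
- Baseline LVEF 64±5 and 12-month SD 6. These values appear in Protocol 2.1 b for a breast cancer cohort; carrying them over to lymphoma is an assumption.
- Correlation of baseline with 12-month LVEF 0.5. This is assumed.
- Within-arm correlation r between ECV change and 12-month LVEF, with a higher ECV going with a lower LVEF. The documents give no value, so a range is shown.

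| Within-arm r | Linear, arm and baseline LVEF | Logistic, arm-adjusted | Logistic as written, no arm |
|---|---|---|---|
| 0.2 | 49% | 22% | 43% |
| 0.3 | 85% | 42% | 61% |
| 0.4 | 99% | 67% | 83% |

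At r = 0 the linear model rejects 5% of the time and the logistic model as written rejects 12%.

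**5. Hand check of the linear column.** If ECV change is independent of baseline LVEF within arm, the partial correlation is r/√(1 − 0.5²), and power is about Φ(atanh(partial r) × √(72 − 3 − 2) − 1.96). For r = 0.2, 0.3 and 0.4 the partial correlations are 0.231, 0.346 and 0.462, giving 49%, 84% and 98%. This agrees with the simulation.

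**The case against.** The strongest reply is that the logistic model is the right one for the question asked. Sections 1.0, 1.3 and 13.1 all name AIC as the event to be predicted, and AIC is a recognised clinical threshold. A reader might infer from the hypothesis sentence in Section 1.0 that the plan contradicts itself. It does not, because that sentence stands beside the AIC wording. What remains is that the sentence has no analysis of its own.

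A reader might also infer that Aim 2b as planned will probably return a null result. The documents do not support that. The low power figures belong to an arm-adjusted model that is not in the plan; the model as written has about 61% power at r = 0.3 and 83% at r = 0.4. Part of that power is the between-arm difference, which is why the model rejects 12% of the time at r = 0. If the aim is purely marginal prediction of AIC, that association is real and not a false positive. It still does not show that fibrosis predicts outcome among patients on the same treatment.

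It is also fair to say that the sub-study was sized for Aim 2a, that no power is claimed for Aim 2b, and that every power comparison depends on an assumed correlation and a roughly linear relation. These points limit the severity. They do not supply the missing analysis or the missing arm term.

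**Conclusion.** The point holds as a minor improvement to a secondary sub-study aim. No stated figure is wrong, and the primary analysis is unaffected.

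Three things are established from the documents: about 9 expected events in the base case (about 7 to 14 under other rates), no arm term in a model where the protocol expects treatment to move both predictor and outcome, and no analysis of the Section 1.0 hypothesis despite continuous CMR LVEF in the same patients.

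The size of the gain is conditional. Across r = 0.2 to 0.4 the adjusted linear model has more power than the arm-adjusted logistic model by 27 to 32 points at r = 0.2 and 0.4 (49 − 22; 99 − 67) and by 43 points at r = 0.3 (85 − 42). The 12% rejection rate at r = 0 rests on the 0.8 SD ECV difference being realised.

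A reader might go further and want the linear model to replace AIC as the lead analysis. The documents do not require that. It would change the worded objective from identifying who develops AIC to estimating a slope, which is a debatable trade.

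**What to change.** In Protocol 13.1, Aim 2b, and in the SAP if it is extended to Aim 2:

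1. Add a prespecified linear regression of 12-month CMR LVEF on the 0 to 6 month ECV change, adjusted for baseline LVEF and treatment arm, as the test of the Section 1.0 hypothesis.
2. Keep the logistic model for AIC as the analysis of the worded objective. Include arm, and fit it by penalised likelihood (for example Firth), because events are few and the statin arm may have none.
3. State the expected event count, about 9 in the base case, so that a null logistic result is read accordingly.

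The cost is wording and one more secondary analysis, reported in LVEF points. No additional patients, scans or visits are needed.

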**Specific Aim 3:**

**Early clinical identification of patients at high risk of AIC.** We will determine whether an early decrease in myocardial strain or an increase in high-sensitivity troponin *during* anthracyclines (after 4 of 8 standard cycles ( $\approx 3$  months)) can predict subsequent development of AIC at 12 months. We will test:

- d. Whether statins, as compared to placebo, prevent the reduction in strain or the increase in troponin throughout the study period (12 months).
- e. Whether a change in troponin, strain, or both at 3 months predicts AIC at 12 months.
- f. Whether a change in troponin, strain, or both at 3 months predicts fibrosis detected by ECV at 6 months.

**Statistical Analysis:**

**Aim 3a. Assumptions:** Based on existing literature and our prior data, our assumption is that the decrease in strain after 4 cycles of chemotherapy ( $\approx 200\text{mg}/\text{m}^2$  dose) in the placebo group will be  $9\pm 10\%$ .

**Sample Size and Power:** with a type I error of 0.05, a sample of 270 patients will have a power of 0.99 to detect a statin effect if there is no change in strain in the statin group and a power of 0.96 if the decrease in strain in the statin group is 50% less than that of the placebo group (9% in the placebo group and 4.5% in the statin group). **Analysis Plan:** We will first characterize the distribution and time course of strain and troponin in patients who do or do not reach the primary outcome (significant change in LVEF at 12 months on CMR as defined in Aim 1) using descriptive statistics. As troponin levels at baseline, 4 cycles and their changes do not follow normal distributions, they will be log transformed. To study the effect of statins on the time trends of strain and troponin, we will use a mixed-design ANOVA model to test for differences between the groups while incorporating repeated strain and troponin measurements at 0, 4 cycles and 12 months.

**Aim 3b. Analysis Plan:** The predictive value of the change in strain and/or troponin after 4 cycles for a significant change in LVEF on CMR at 12 months (primary endpoint of Aim 1) will be explored using a mixed design ANOVA model. A multivariable logistic regression model will then be applied, entering strain and troponin as variables. The model may be adjusted for additional key variables such as clinical univariate predictors and change in echocardiographic LVEF.

**Aim 3c. Analysis Plan:** The predictive value of the change in strain and/or troponin after 4 cycles for the change of fibrosis (assessed by ECV) at 6 months will be explored using a mixed-design ANOVA model. The model may be adjusted for additional key variables such as clinical univariate predictors and change in LVEF.

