### 13.2 Sample Size, Accrual Rate and Study Duration

**Feasibility:** In 2012, there were 412 patients with lymphoma treated with anthracyclines at MGH, DFCI and BWH (110 at MGH and 312 at DFCI and BWH). In the large cohort of lymphoma patients that we reported in our preliminary data, only 8% of patients ( $n=33$ ) were on statins at the time of chemotherapy and would be excluded. Even using the new more expansive cholesterol guidelines and assuming that all the patients who were eligible to receive statins were treated with statins, more than 80% of patients ( $n=330$ ) would be eligible for enrollment annually. In aggregate, less than 30 of the remaining 330 patients would be excluded based on these criteria and this would leave a final total of 300 patients with lymphoma per year that would meet entry criteria and not meet exclusion criteria. Based on prior trials recruited by this group, we anticipate enrollment of 33% of eligible patients ( $\approx 100$  per year, 8 per month); 5-6 patients per month will be enrolled from DFCI/BWH and 2-3 patients per month from the MGH. We expect a total of about 3 years to complete enrollment.

In total 300 patients need to be enrolled.

Accrual Targets
------------------------

Ethnic Category	Sex/Gender			
	Females		Males	Total
Hispanic or Latino	25	+	26	= 51
Not Hispanic or Latino	125	+	124	= 249
Ethnic Category: Total of all subjects	150 (A1)	+	150	= 300
Racial Category				
American Indian or Alaskan Native	0	+	0	= 0
Asian	16	+	15	= 31
Black or African American	14	+	13	= 27
Native Hawaiian or other Pacific Islander	0	+	0	= 0
White	115	+	117	= 232
Racial Category: Total of all subjects	150(A2)	+	150 (B2)	= 300 (C2)

(A1 = A2)

(B1 = B2)

(C1 = C2)

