**Primary End-Point**

**Our primary endpoint will be the proportion of patients in each group that have a decrease of 10% or more in LVEF to <55% from baseline to 12 months after initiation of anthracyclines.**

*Assumptions for Sample Size Calculation:* We anticipated that 20% of the patients in the placebo group will reach the primary end-point. This assumption is based on significant prior literature; specifically, Limat *et al.* performed a prospective study where they enrolled patients similar to those proposed in this study (lymphoma receiving anthracycline-based chemotherapy) and performed a baseline measurement of LVEF and a measurement at 1 year. Their primary end-point was a more stringent cut-off than recommended by guidelines or being used in this study, a decrease of >15% in LVEF. They found that 20% of their population had a reduction of >15% in LVEF. Using CMR, two studies have tested the percentage of patients with a significant reduction in LVEF after anthracyclines. In a prospective observational study, Drafts and colleagues found that 26% of patients decreased their LVEF to <50% and in a prospective randomized study, Bosch and colleagues found that up to 33% of patients decreased their echocardiographically-derived LVEF to <55%. In the single small, randomized study which also used 40 mg of atorvastatin with 20 subjects in each arm, there was no decrease in LVEF after anthracyclines among patients on statins.

Our base case assumptions are as follows: 20% of the placebo group and 5% of the statin treatment group will meet the primary endpoint and we will be able to enroll 300 patients meeting all inclusion and exclusion criteria. From these, we anticipate a drop-out rate of approximately 10% due to a one-year mortality of  $\approx$ 5-6% and atorvastatin related side-effects

in 4-5% of patients. The remaining 270 patients will provide us with a > 90% power to detect a 15% difference in the proportions of those achieving the primary end-point at a two-sided significance level of 0.05. Moreover, we will have a 70% power if the difference in the percentage reaching the primary end-point between groups falls as low as 10%.

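### Aim 3a's mixed-design ANOVA treats baseline as an outcome and names neither the tested term nor a missing-visit rule; a baseline-adjusted likelihood-based model would use the same data more precisely

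*Protocol*

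**What the plan says.** Protocol section 13.1, Specific Aim 3, Aim 3a, gives the whole plan for this comparison. The model is named in one sentence, "we will use a mixed-design ANOVA model to test for differences between the groups", and its repeated measurements are those at 0, 4 cycles and 12 months. Troponin is log transformed.

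Power is given for strain only. The assumed fall in the placebo arm is 9 with SD 10, and "with a type I error of 0.05" the protocol states that "a sample of 270 patients will have a power of 0.99 to detect a statin effect" if strain does not change on statin. It also claims "a power of 0.96 if the decrease in strain in the statin group is 50% less than that of the placebo group", that is, "9% in the placebo group and 4.5% in the statin group". Whether the test is one- or two-sided is not stated for this aim.

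On losses, section 13.2 says "In total 300 patients need to be enrolled", and the SAP (Primary End-Point, assumptions) says "we anticipate a drop-out rate of approximately 10" percent. The protocol attributes this to about 5% one-year mortality and 4% atorvastatin side-effects; the SAP gives 5-6% and 4-5%. The primary analysis plan in section 13.1 asks for intent-to-treat analyses and 1-year imaging in every patient. Nothing is said about missing visits in Aim 3, and the SAP ends at Aim 1c.

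**The concern.** Three choices are left open or made inefficiently.

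- **Baseline is an outcome.** Randomisation makes the expected baseline difference zero. Using baseline as a covariate removes between-patient variation; using it as a third outcome does not do so in the same way.
- **The tested term is not named.** A test of differences between groups can mean the group main effect, which averages in a visit where no effect can exist, or the group-by-time interaction. The two can differ greatly in power.
- **The fit and the missing-visit rule are not stated.** Classical least-squares mixed-design ANOVA needs all three values per patient. Someone who dies before 12 months would then also lose the 4-cycle value, which is the time point Aim 3 is built on.

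Leaving these open allows the choice to be made after the data are seen.

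**Working it through.** **Inputs from the documents.** 270 patients, 135 per arm (Aim 3a; section 1.0: "randomized 1:1 to atorvastatin 40mg/daily or placebo"); difference 9 − 4.5 = 4.5; SD 10, taken as the SD of change; type I error 0.05. **Assumed.** Two-sided test; equal correlation ρ between visits of 0.3, 0.5 or 0.7, with the SD of change held at 10. Powers use the normal approximation; the t distribution lowers them by about 0.001.

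**1. The plan's own figures.** SE = 10 × √(2/135) = 1.217.
- Difference 4.5: Φ(4.5/1.217 − 1.960) = Φ(1.737) = 0.959, against 0.96 stated.
- Difference 9: above 0.9999, against 0.99 stated.
- One-sided 0.05 would give 0.980 for 4.5, so two-sided fits better.

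The stated power is thus that of a two-sample comparison of one change score, not of a three-visit ANOVA.

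**2. Baseline as covariate at 4 cycles.** Visit SD s = 10/√(2(1 − ρ)). Residual SD = s√(1 − ρ²) = 10√((1 + ρ)/2).

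| ρ | Residual SD | SE | Power |
|---|---|---|---|
| 0.3 | 8.06 | 0.981 | 0.996 |
| 0.5 | 8.66 | 1.054 | 0.990 |
| 0.7 | 9.22 | 1.122 | 0.980 |

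**3. Which ANOVA term.** Take a difference of 4.5 at both post-baseline visits.

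*Group main effect:* the expected difference is (0 + 4.5 + 4.5)/3 = 3.0, and the variance of a patient's mean is s²(1 + 2ρ)/3.

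| ρ | Variance | SE | Power |
|---|---|---|---|
| 0.3 | 38.1 | 0.751 | 0.98 |
| 0.5 | 66.7 | 0.994 | 0.86 |
| 0.7 | 133.3 | 1.405 | 0.57 |

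*Group-by-time (2 df, compound symmetry):* deviations of the differences from their mean are −3, 1.5 and 1.5, with sum of squares 13.5; s²(1 − ρ) = 50. Noncentrality = (135/2) × 13.5/50 = 18.2, giving power 0.975 at every ρ.

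**4. Deleting incomplete patients (change score, difference 4.5).**
- 300 × 0.9 = 270: 0.959, the plan's own figure.
- A further 10% missing (243): 0.939.
- A further 20% missing (216): 0.911.

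**5. Bias in the complete-case estimate.** Large simulations with a true difference of 4.5, visit SD 10, and assumed correlations of 0.5 (baseline with 4 cycles), 0.7 (4 cycles with 12 months) and 0.3 (baseline with 12 months). Estimates are for 4 cycles unless stated.
- One logistic drop-out rule for both arms, 11% missing overall: 4.39 if the odds rise 1.65-fold per 10-point fall in strain, about 4.2 if 2.7-fold. With 5% missing and 2.7-fold: about 4.3.
- Same dependence on 4-cycle strain in both arms, with the drop-out rate held at 10% in each: 4.49, so essentially no bias.
- Dependence in the placebo arm only: 4.13 with 10% missing and 3.78 with 20%; at 12 months, 4.35 and 4.21. Across the mechanisms tried with 5-11% missing, the placebo-only estimate ranged from about 3.4 to 4.3.
- Likelihood-based estimates using all available values stayed at about 4.5 in the equal-rate and placebo-only runs.

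**The case against.** A reader might infer that the plan drops every patient with a missed visit, and so loses material power and biases the result. The documents do not support that.

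- **Case deletion is not written.** It follows from the classical way of fitting the named method. A model under the same label can be fitted by likelihood using every visit. The intent-to-treat wording and the 1-year imaging of all patients point away from deliberate deletion.
- **Planned drop-out is already counted.** The 270 is what remains of 300 after about 10% loss, and step 4 shows that deletion beyond that is cheap at the plan's effect size.
- **Baseline among the outcomes does not by itself invalidate or weaken the test.** The group-by-time test remains valid, and its 0.975 is slightly above the stated 0.96. The protocol speaks of time trends, which suggests that term.
- **The bias needs a mechanism the documents do not give.** They attribute drop-out to mortality and statin side-effects, and link neither to an earlier fall in strain. Patients with statin toxicity are to stay in the analysis.

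All of this stands. It does not remove the gap: intent-to-treat says who is analysed, not what to do when a value cannot exist because the patient died, and no passage settles the term or the fit.

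**Conclusion.** The point holds as a matter of specification and efficiency. Aim 3a takes baseline as one of three outcomes, does not name the tested term, and has no rule for missing visits although deaths make some certain.

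At the plan's 4.5 difference, baseline adjustment raises power from 0.96 to between 0.980 and 0.996. Reading the test as a group main effect could lower it to as little as 0.57. These figures rest on assumed correlations of 0.3 to 0.7; the main-effect figures also assume an effect sustained to 12 months. The loss from case deletion alone is small.

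Bias toward understating the statin effect is possible, not shown: a true 4.5 would be estimated as about 4.2 to 4.5 under a common drop-out rule, and lower if only placebo drop-out depends on strain. No power is given for troponin, so its part cannot be sized. Because this is a secondary aim, the priority is modest.

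**What to change.** Replace the ANOVA in Aim 3a with a likelihood-based mixed model for repeated measures, for strain and for log troponin:

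- outcomes: the 4-cycle and 12-month values;
- factors: arm, visit and arm-by-visit;
- covariates: baseline value and baseline-by-visit;
- unstructured covariance;
- named arm-by-visit contrasts at 4 cycles and 12 months, with the sidedness of the test stated;
- every randomised patient with at least one post-baseline value.

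State that the 12-month contrast assumes data missing at random. Part of the loss is death, and the model would implicitly estimate strain for patients who have died, so add a sensitivity analysis for deaths.

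When naming the early visit, reconcile its timing: Aim 3 puts it after 4 cycles, while sections 9.1 and 10 put it after 3.

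The cost is a paragraph in section 13.1 or in the SAP, which does not yet cover Aim 3, and standard software. No extra patients, visits or measurements are needed.
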